#### 2.0 Rationale and Objectives

#### Rationale:

The ratio of Ang(1-7) to AngII, is reduced in both IPAH and HPAH patients. This difference is primarily driven by decreased Ang(1-7), rather than increased AngII, suggesting that ACE2 is suppressed in idiopathic and heritable PAH. Additionally, we have published therapeutic benefit of ACE2 in a transgenic mouse model of human heritable PAH. Because of this data showing decreased ACE2 in PAH patients, the demonstrated safety of ACE2 use in normal humans, and the strong efficacy data in mice, it would appear to be prudent and timely to test ACE2 in PAH patients. **The strategy is** to develop rhACE2 clinically for the treatment of pulmonary arterial hypertension; however, before pursuing a large scale treatment trial, a dose-finding, tolerability, and safety study in this patient population is warranted.

#### Objectives:

#### 2.1 Primary Objective

The primary objective of the study is to determine safety of rhACE2 when administered as a single dose or multiple doses intravenously to subjects with PAH receiving background PAH-specific therapy.

#### 2.2 Secondary Objectives

The secondary objective of the study is to evaluate changes in biomarkers of disease (BNP, AngII/Ang (1-7), serum soluble IDH, serum NO, cardiac troponin I, SOD2 activity, urine isoprostanes and isofuranes) in subjects with PAH receiving rhACE2. We will also evaluate changes in pulmonary and systemic hemodynamics and echocardiographic markers of right heart function in patients receiving rhACE2.

#### 3.0 Animal Studies and Previous Human Studies (IB)

We have used an animal model of heritable PAH and tested the effects of a six week infusion of rhACE2. We found marked reduction in pulmonary hypertension with microarray data from lung showing improvement in cytoskeletal function (Johnson J et al, AJP Lung 2012). In human studies, we have looked for alterations in the Ang II/Ang (1-7) ratio and found reduced plasma Ang (1-7) and reduced Ang II/Ang (1-7),

suggesting reduced function of ACE2 in pulmonary arterial hypertension. Other groups have had similar findings in rodent models (Shenoy V et al, Hypertension 2014, Shenoy et al, AJRCCM 2013). Aperion Pharmaceuticals (who owned the compound prior to GSK) has previously conducted safety trials in healthy subjects: 5 subjects at 0.1 mg/kg, and 4 each at 0.2 mg/kg, 0.4 mg/kg, and 0.8 mg/kg, then three repeated doses, then six repeated doses, at 0.4 mg/kg in three subjects. There were no clinically significant abnormal labs or vital signs in any patient. There were 4 adverse events (AEs), 3 of which occurred in the two lowest doses; all were mild and resolved without a need for intervention and without any sequelae. GSK has an ongoing trial of ACE2 administration in acute respiratory distress syndrome with three days of twice daily infusions. While the trial is ongoing and efficacy data is not available, they have not found any significant or severe adverse events related to study drug administration (personal communication 11/24/14, [name]).

#### 4.0 Study Design:

This is a Phase 1, single center, open-label, dose-escalation in subjects with PAH whose symptoms have been clinically stable for 8 weeks prior to enrollment and have had no change in PAH-specific therapy 12 weeks prior to enrollment. Eligible subjects will undergo baseline assessments before beginning treatment with rhACE2.

#### **PHASE A: Single Dose Escalation:**

The dose escalation will follow the traditional 3+3 design. Briefly, the first cohort of 3 subjects will be treated at dose 0.2mg/kg. If none of the 3 subjects experiences a dose limiting toxicity (DLT), another three subjects will be treated at the next higher dose. Since ACE2 has been administered to human subjects at a lower dose and we plan to start at a safe dose of 0.2mg/kg, we will not follow the Fibonacci sequence to avoid a rapid increase of dose.

Instead, we fix the increment at 0.2-0.4mg/kg, i.e. the dose will be 0.2, 0.4, 0.8, to a maximum of 1.2. If one of the first 3 subjects experiences a DLT, three more subjects will be treated at the same dose level. The dose escalation continues until at least two subjects of 3 to 6 subjects experience DLT. The dose right below this toxic dose level will be considered the maximum tolerated dose (MTD). If we reach 1.2 mg/kg and there is no identified toxicity, which is quite possible given the prior experience, we will assess for 50% increase in Ang(1-7):AngII ratio to ensure biochemical efficacy.

During the treatment period, the planned rhACE2 dose-escalation regimen for the initial 12 subjects is as follows:

- First 3 subjects will receive rhACE2 intravenously at 0.2 mg/kg, if no dose limiting toxicities are noted:
- Next 3 subjects will receive rhACE2 intravenously at 0.4 mg/kg, if no dose limiting toxicities are noted:
- Next 3 subjects will receive rhACE2 intravenously at 0.8 mg/kg, if no dose limiting toxicities are noted:
- Next 3 subjects will receive rhACE2 intravenously at 1.2 mg/kg, if no dose limiting toxicities are noted:

Study design will follow the Up-and-down design. If  $\mathbf{0}$  of  $\mathbf{3}$  patients experiences a dose-limiting toxicity (DLT), the dose is **escalated**. If  $\mathbf{1}$  of  $\mathbf{3}$  patients experiences a DLT,  $\mathbf{3}$  additional patients are treated at the same dose. If **none** of the additional patients develops a DLT, the dose is escalated; otherwise escalation ceases. If  $\mathbf{\geq} 2$  of  $\mathbf{3}$  or  $\mathbf{\geq} 2$  of  $\mathbf{6}$  patients experience a DLT, the maximum tolerated dose (MTD) has been exceeded. Dose limiting toxicities are defined as toxicities that, due to their severity or duration, are considered unacceptable, and limit further dose escalation. Examples of DLT's:

- Severe headache unrelieved by NSAIDS
- Nausea/Vomiting
- Hypotension as defined by mean arterial pressure <60mmHg or a drop in systolic blood pressure of 25%
- Changes in echocardiogram suggesting worsening right ventricular function rhACE2 will be administered in the Cardiac Catheterization lab or the Cath lab holding area where the participant will be monitored for 4 hours following dosing with pulmonary arterial catheter in place. After four hours, the catheter will be removed. Transpulmonary blood will be collected from the mixed venous position and the wedge position at baseline and four hours after drug administration prior to removal of the catheter. Study participants will then be admitted to the Clinical Research Center (CRC) for further monitoring for a total of 24 hours post dosing. Hemodynamics will be measured at time points described in the schedule of events. After 24 hours from drug administration, patients will be discharged from the CRC. For each dosing group, an acceptable safety profile at each dose level will be required prior to dose escalation. In addition, the safety profile of the planned dose-escalation regimen will be evaluated throughout the study. Subjects will return after a two-week washout period for follow-up assessments.

Enrollment will continue until 12 subjects have completed the washout period and followup assessments.

If no safety concerns have been identified in the dose escalation phase, the multiple phase dosing will proceed as described below using one dose below the maximal tolerated dose of the single dose phase or at 1.2mg/kg if no MTD is reached.

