#### Role of GSK in Study:

[figure not shown]
GSK was not involved in the development or implementation of the protocol nor was the company involved in data analysis. GSK provided study drug (GSK2586881) but did not participate in collection of data. GSK performed RAS peptide analysis given their expertise in this area. Finally, GSK performed PK/PD studies and immunogenicity studies. The remainder of the assays were performed by the study investigators. \_GSK did not provide funding for the study.

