#### 7.5 Electrocardiogram

In subjects with PAH, the electrocardiogram (ECG) typically reveals right axis deviation and right ventricular (RV) hypertrophy. The standard 12-lead ECG will be recorded while the subject is resting in supine position. The following parameters will be assessed: HR, RR, PQ, QRS, QT and QTc. Additionally, the occurrence of de- or repolarization disorders, arrhythmic disorders or other abnormalities will be assessed and obvious changes of ECG parameters compared to the baseline record will be commented upon. ECGs will be interpreted locally. Changes to the ECG will be coded by the Investigator as clinically significant or not clinically significant. Clinically significant changes will be reported as AEs. Original printouts will be archived within the subject file and ECG recording results will be noted in the subject's CRF.

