#### 7.6 **Echocardiogrophy**

Two-dimensional (2D) and Doppler echocardiography will be performed using standard techniques on commercially available equipment with a predefined imaging protocol. Images will be obtained with the subjects in the left lateral position. The maximal tricuspid regurgitant jet (TRJ) velocity will be assessed by determining the peak regurgitant velocity (v) in the continuous-wave Doppler flow profile obtained from the cardiac apex. The tricuspid valve pressure gradient (TPG) (i.e., the pressure difference

between the right ventricle and right atrium during systole) will be calculated by applying the modified Bernoulli equation. Pulmonary arterial systolic pressure will be calculated using the formula  $4v^2$  + right atrial pressure. Right atrial pressure will be assessed by clinical examination of the jugular venous pressure, and echocardiographic diameter of the inferior vena cava and its change with inspiration.

The right atrial volume is calculated at end systole from the apical four chamber view using the diameter and the long axis length of the atrium according to the equation: Volume = (7(pi x D²L)/6, where D = minor axis (cm), L = major or long axis (cm) (Wang 1984, Chest). The eccentricity index, a measure of the degree of septal displacement, will be measured at end diastole and end systole from parasternal short-axis projections of the left ventricle. It is calculated as the ratio of the minor axis of the left ventricle parallel to the septum at the level of the chordae (a), divided by the minor axis perpendicular to and bisecting the septum at the same section (b) (eccentricity index = a/b). The Doppler-derived RV MPI is calculated as described previously by Tei et al (Tei 1996, J.Am.Soc.Echocardiogr.) using the length of two time intervals in the formula (a-b)/b, where a equals the time between the onset of QRS complex and onset of tricuspid inflow and b equals the ejection time of RV outflow. TAPSE will be measured as per protocol (Forfia et al, AJRCCM, 2006).

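### The right-heart echo endpoint is an uncontrolled baseline-to-24 h comparison of operator-dependent readings, and the plan does not specify a reader masked to time or dose

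*Combined protocol and SAP*

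**What the plan says.** Section 4.0 sets the design: "This is a Phase 1, single center, open-label, dose-escalation in subjects with PAH". No control arm is described.

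Echocardiography has two uses:
- **Secondary endpoint.** Section 2.2 lists "echocardiographic markers of right heart function in patients receiving rhACE2". Section 12 analyses secondary endpoints as paired change over time with mixed-effects models, concedes that the sample size limits inference, and states no alpha.
- **DLT example.** Phase A lists "Changes in echocardiogram suggesting worsening right ventricular function", with no named measurement, cut-off or reader.

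The single-dose schedule (Appendix 2) places echo at baseline and at 24 hours only. Section 7.6 says that imaging "will be performed using standard techniques on commercially available equipment with a predefined imaging protocol". It then defines tricuspid regurgitant (TR) jet velocity, right atrial (RA) volume, eccentricity index, myocardial performance index (MPI) and TAPSE. It adds that "Right atrial pressure will be assessed by clinical examination of the jugular venous pressure", together with the appearance of the inferior vena cava. It does not say who measures, or whether that person knows the time point or dose.

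**The concern.** Every subject's pair runs in the same order, pre-dose then post-dose, and everyone at the site knows the dose. The measurements require an operator to choose a beat, place a caliper or outline a border. If the operator expects improvement, or fears harm, small choices can lean the same way in each subject. Such a lean adds a constant to the mean paired change. It does not average out with more subjects, and without a concurrent control it cannot be told apart from a drug effect.

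The same unmasked judgment enters the echo DLT example. There a single call matters: under the 3+3 rule, one DLT among the first three subjects changes the decision from escalating to expanding the cohort.

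**Working it through.** **1. Is masking specified anywhere?** Sections 4.0, 7.6, 10.3, 12 and Appendix 2 were read together.
- Section 7.6 standardises acquisition and formulas, which limits random variation but does not hide time or dose.
- Section 10.3 gives the independent monitor completed case report forms and serious adverse events. That review comes after the reading.
- No central, independent or masked read appears in the text available.

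**2. What could a reading shift do to the paired change? (illustration)**

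Inputs: Supplemental Table 5 gives TAPSE 2.2 at baseline and 2.4 at 24 hours, p = 0.31. The planned number is 4 dose levels × 3 subjects = 12, as Phase A states.

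Assumptions: a two-sided paired t-test; n = 5 in Table 5; two-sided alpha 0.05; constant shifts of 0.1 and 0.2 cm. None is stated in the documents. The n = 5 is suggested by Supplemental Table 7, where all but one of the pressure and heart-rate means are multiples of 0.2.

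- t with 4 df at two-sided p = 0.31 is 1.16.
- SD of the paired difference = (0.2 / 1.16) × √5 = 0.385 cm.
- Noncentrality at n = 12 = shift × √12 / 0.385, which is 0.90 for 0.1 cm and 1.80 for 0.2 cm.
- Probability of exceeding the critical value 2.201 (11 df) with no drug effect: 13.1% and 37.6%.

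The TAPSE means are rounded to 0.1, so the true change could lie between about 0.1 and 0.3 cm:

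| Mean change (cm) | SD of difference (cm) | 0.1 cm shift | 0.2 cm shift |
|---|---|---|---|
| 0.1 | 0.19 | 37.6% | 90.5% |
| 0.2 | 0.385 | 13.1% | 37.6% |
| 0.3 | 0.58 | 8.5% | 19.5% |

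If Table 5 held 12 subjects instead, t (11 df) = 1.06, SD = (0.2 / 1.06) × √12 = 0.65 cm, and a 0.1 cm shift gives about 8%.

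More subjects do not help. With the central SD, the rates at n = 5 are about 7% and 15%, lower than at n = 12, because a constant bias becomes easier to detect as n grows.

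**3. How sensitive is escalation to an echo call? (illustration)**

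Under the stated rule, P(escalate) = P(0 of 3) + P(1 of 3) × P(0 of 3). Take an assumed DLT probability of 0.10 per subject: 0.729 + 0.243 × 0.729 = 0.906. If false echo calls occurred in an assumed 10% of subjects, the probability becomes 1 − 0.9 × 0.9 = 0.19 and P(escalate) falls to 0.730. Missed echo DLTs would push the other way. Neither rate comes from the documents.

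**The case against.** **Silence is not proof of unmasked reading.** Correct. The documents do not say that the echo reader knows time and dose; they do not specify otherwise. The point is a gap in the plan, not evidence that any reading was biased.

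**This is a small Phase 1 trial with descriptive aims and no alpha.** This stands against treating the percentages as the trial's error rate. It does not remove the bias, which affects a descriptive mean change just as much.

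**The DLT call is broader than a caliper reading.** This also stands. DLTs are defined by unacceptable severity or duration, echo is one of several examples, and catheter haemodynamics give right-heart data independent of echo. A reader might infer that a 0.1–0.2 cm shift in TAPSE passes straight into the escalation decision. The documents do not support that. The catheter is, however, removed at four hours, so it does not corroborate the 24-hour echo.

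**Do ECG and peptides have the same problem?** A reader might infer so, but the documents do not support it. It is true that "ECGs will be interpreted locally", with the investigator coding changes against the baseline record. But ECG is neither a listed DLT example nor a named secondary endpoint, and its safety use requires that comparison. The angiotensin ratio comes from an instrumental assay: mass spectrometry with labelled internal standards, or radioimmunoassay. The supplement says "GSK performed RAS peptide analysis given their expertise in this area", but it also says that the company took no part in collecting or analysing the data. Coding research tubes is optional good practice, not part of this concern.

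**Shuffling clips cannot mask everything.** Agreed. Right ventricular function on echo is an eligibility criterion, so the reader may already have seen the baseline study. The bedside jugular estimate cannot be masked at all. The fix allows for both.

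**Conclusion.** The concern holds for the echo endpoint measurements. The design is open-label and uncontrolled, the order is always before then after, the measurements depend on the operator, and no masking to time or dose is specified. The same judgment enters an echo DLT example that has no stated parameter.

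The documents do not fix the size of the effect. Under the assumptions above, shifts of 0.1 and 0.2 cm would turn a nominal 5% test into about 13% and 38%, with ranges of 8.5–37.6% and 19.5–90.5% for rounding alone. These figures show only that modest shifts matter against this spread; they do not estimate what happened or the plan's own error rate.

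This is a cheap improvement. It does not invalidate the design, and it does not remove the other weaknesses of an uncontrolled before-after comparison.

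**What to change.** Add a paragraph to section 7.6:

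- The existing reader measures TAPSE, TR jet velocity, eccentricity index, RA volume and MPI for the endpoint analysis in a session separate from the clinical read, for example at the end of each dose cohort.
- Stored clips carry a code only, with date, time, dose and subject identifiers removed, and are read in random order across subjects. A cohort of three gives 3 × 2 = 6 studies.
- Measurements are locked before unmasking. Where timing allows, this is done before the cohort's escalation review so that it can inform that review.
- The real-time clinical and DLT read stays unmasked and is not delayed.
- The right atrial pressure estimate is reported as unmasked, as is the pulmonary pressure calculated from it.

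Limits: reading by cohort hides time well but dose only partly, because all studies in a batch share one dose. Some recognition of a baseline study seen earlier is also possible.

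Cost: one additional measurement session per batch and some relabelling, with no extra reader, scan or visit.

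### Phase A enrolment is set unconditionally at 12 completers, but the plan's own 3+3 rule can use anywhere from 3 to 24 subjects; 12 is only the no-DLT case

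*Combined protocol and SAP*

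**What the plan says.** All the relevant text is in section 4.0, Phase A (Single Dose Escalation).

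- **Design:** "The dose escalation will follow the traditional 3+3 design".
- **Dose levels (mg/kg):** "i.e. the dose will be 0.2, 0.4, 0.8, to a maximum of 1.2", so four levels.
- **0 of 3 with a DLT:** "If none of the 3 subjects experiences a dose limiting toxicity (DLT), another three subjects will be treated at the next higher dose".
- **1 of 3 with a DLT:** "If one of the first 3 subjects experiences a DLT, three more subjects will be treated at the same dose level".
- **After an expansion:** if none "of the additional patients develops a DLT, the dose is escalated; otherwise escalation ceases".
- **Stop:** "The dose escalation continues until at least two subjects of 3 to 6 subjects experience DLT".
- **Planned regimen:** "the planned rhACE2 dose-escalation regimen for the initial 12 subjects is as follows". Three subjects are then listed at each of the four levels, each line with a no-DLT proviso.
- **End of enrolment:** "Enrollment will continue until 12 subjects have completed the washout period and followup assessments". No condition is attached.

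The section gives no range or maximum for Phase A, and does not say whether the rule or the count governs when they differ. Section 12 (Statistical Considerations) gives no basis for the sample size.

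**The concern.** A 3+3 design does not have a fixed sample size. The number treated depends on the DLTs seen, so a fixed count can agree with the rule only on some paths. The enrolment sentence drops the no-DLT condition that the planned regimen carries.

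Followed to the letter, the count can override the rule in two directions. It can close Phase A while the rule still calls for a further cohort. It can also call for more subjects after the rule has ended escalation.

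The result of the escalation, either an MTD or the top level completed without one, bears on the primary safety objective (section 2.1). The last paragraph of Phase A also takes the multiple-dose phase from that result. A count that cuts escalation short would leave the result undefined.

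**Working it through.** **1. The plan's figure.** Four levels × 3 subjects, no DLT at any level: 4 × 3 = 12. The stated figure is reproduced on this path.

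**2. Range under the rule.** Each level opened uses 3 subjects (0/3, or at least 2/3) or 6 (1/3, then expansion).

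- Minimum: at least 2/3 with a DLT at the first level gives 3.
- Maximum: all four levels expanded gives 4 × 6 = 24.
- Possible totals: 3, 6, 9, 12, 15, 18, 21, 24.

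This counts treated subjects. It assumes no replacement of non-completers, no de-escalation and no filling of the MTD level to six, because the documents state no such rule.

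**3. Exactly one DLT.** One level uses 6 and the other three use 3 each: 6 + 3 × 3 = 15, whichever level it is.

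**4. Two or more DLTs.** Each level has two outcomes that continue and two that stop. That gives 2⁴ = 16 paths through all four levels and 2 × (1 + 2 + 4 + 8) = 30 paths that stop on the way, 46 in all. One path has no DLT. Of the other 45, five end at 12:

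- 0/3, 0/3, 0/3, then ≥2/3
- 0/3, 0/3, then 1/3 followed by ≥1/3
- 0/3, 1/6, then ≥2/3
- 1/6, 0/3, then ≥2/3
- 1/6, then 1/3 followed by ≥1/3

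**5. A literal stop at 12.**

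- One expansion, at levels 1 to 3: 6 + 3 + 3 = 12. Level 4 (1.2 mg/kg) is never opened and no MTD is found.
- One expansion, at level 4: 3 + 3 + 3 + 3 = 12. Level 4 is open but its second three subjects are not treated.
- Toxicity stop at 3, 6 or 9 subjects: the sentence asks for 9, 6 or 3 more, with no dose level assigned.

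**6. How often the rule and the count differ.** The documents give no DLT rate, so a constant rate p at all four levels is assumed. Per level:

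- a = (1−p)³: 0/3, escalate, 3 subjects
- e = 3p(1−p)² × a: 1/3 then 0/3, escalate, 6 subjects
- c = 3p(1−p)² × (1−a): 1/3 then ≥1/3, stop, 6 subjects
- d = 3p²(1−p) + p³: ≥2/3, stop, 3 subjects

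Then

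- P(N=12) = a⁴ + a³d + a²c + 2aed + ec
- P(N<12) = d + (ad + c) + (a²d + ac + ed)
- P(N>12) = 1 − P(N=12) − P(N<12)

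Example, p = 10%: a = 0.729, e = 0.1771, c = 0.0659, d = 0.028.

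- P(N=12) = 0.2824 + 0.0108 + 0.0350 + 0.0072 + 0.0117 ≈ 0.347
- P(N<12) = 0.0280 + 0.0863 + 0.0678 = 0.182
- P(N>12) = 1 − 0.347 − 0.182 = 0.471

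| Assumed DLT rate | P(N=12) | P(N>12) | P(N<12) | Expected N |
|---|---|---|---|---|
| 5% | 56% | 38% | 6% | 13.1 |
| 10% | 35% | 47% | 18% | 12.9 |
| 15% | 24% | 42% | 34% | 12.0 |
| 20% | 19% | 32% | 49% | 10.7 |

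With rates rising 5/10/20/30% across the four levels, the figures are 33%, 50% and 18% (rounded), with expected N 13.4.

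**The case against.** The best defence is that the section already marks 12 as the no-DLT plan. It speaks of an initial 12 subjects, puts a no-DLT proviso on every step, and says that finding no toxicity is quite possible. The expansion and stopping rules are explicit and appear twice. An acceptable safety profile is required before each escalation, and section 10.3 provides an independent monitor who advises on continuing or terminating. On this reading the enrolment sentence is a loose summary, and a sensible site would follow the rule. Most of this stands, and it limits the severity. It does not remove the conflict: the sentence carries no condition, and the word *initial* implies that more subjects may follow, which a stop at 12 does not allow for.

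Four stronger readings are tempting but not supported.

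- **That 12 fails as soon as any DLT occurs.** This is exact only for exactly one DLT. Five multi-DLT paths end at 12, one of them after stopping at the top level.
- **That the rule and the count agree only with probability (1−p)¹²**, that is 54, 28, 14 and 7% at the four rates. This is the no-DLT probability. It leaves out the paths that stop for toxicity at 12, so it understates the agreement.
- **That the plan permits dosing at a higher level after escalation has ceased, or would carry 1.2 mg/kg into the next phase untested.** Nothing allows the first. The second follows only if the count is read as overriding the rule, and the move to multiple dosing is also conditional on no safety concerns, with the monitor determining the multiple-dose dosage.
- **That consent, ethics or drug-supply numbers are wrong.** The documents reviewed show no such figures, so this cannot be checked.

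**Conclusion.** The concern holds as a conflict between a stated size and stop rule and the plan's own escalation design. The range of 3 to 24, and the total of 15 after exactly one DLT, follow from the rule alone, under the counting assumptions in step 2 of the working.

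The probabilities rest on assumed DLT rates and show scale only. Across constant rates of 5 to 20%, the rule ends on a number other than 12 in 44 to 81% of trials (100 − 56 and 100 − 19). The direction shifts from mostly more than 12 at the low rates to mostly fewer at 20%. The maximum of 24 is possible but rare, with probability at most 0.3% over these rates.

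Since the intended meaning can be recovered from the surrounding text and the escalation rule is usable as stated, this is a wording reconciliation, below must-fix.

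**What to change.** Reconcile the two statements in section 4.0 by replacing the enrolment sentence with text such as:

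*Phase A enrolment ends when the 3+3 rule ends and the treated subjects have completed washout and follow-up: 12 subjects if no DLT occurs, fewer if escalation stops early, at most 24.*

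Use the range 3 to 24 wherever the Phase A size is stated. A range of 12 to 24 would be wrong, because two or more DLTs in a first cohort of three can end the rule at 3, 6 or 9 subjects without any expansion.

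The cost is protocol wording. Every expansion is already required by the plan's own rule, so the change adds no subjects beyond what the rule demands. Expected enrolment is about 11 to 13 over the constant rates used above.
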